10. STUDY CALENDAR AND VISIT SCHEDULE

Baseline evaluations are to be conducted within 3 weeks prior to start of protocol therapy.

For the first cohort:

Procedure	Pre-study	Week 1		Week 2		Week 3		Week 4		Week 5		Surgery ^a	Off treatment
		D1	D4-7	D8	D9-14	D15	D16-21	D22	D23-28	D29	D30-32		
Minimum treatment						Optional							
Treatment:													
Entinostat		A		A		A		A		A			
Anastrozole/Tamoxifen			B	B	B	B	B	B	B	B	B		
Clinical assessment:													
Informed consent	X												
Demographics	X												
Medical history	X												
Current medications	X	X		X		X		X		X		X	X
Physical exam	X	X		X		X		X		X		X	X
Vital signs	X	X		X		X		X		X		X	X
Height	X												
Weight	X	X		X		X		X		X		X	X
Performance status	X	X		X		X		X		X		X	X
Adverse event evaluation		X		X		X		X		X		X	X
Tumor measurement ^b	X	X		X		X		X		X		X	
Laboratory test:													
CBC w/diff, plts	X	X		X		X		X		X		X	X
Chemistries ^c	X	X		X		X		X		X		X	X
PT/INR, PTT	X											X	
Electrocardiogram	X												
Pregnancy test ^g	X												
Correlative studies (Research procedures):													
Pharmacokinetic study													
• Pilot phase, stage 1		X ^d				X ^d							
• Stage 2		X ^e				X ^e							
Methylation profile		X ^f										X ^f	
Tumor sample	X											X	

A: Entinostat: as per appropriate dose level PO weekly on day 1, 8, 15, 22 and 29 ± 2 days. Preferably 22 days.

B: Anastrozole for postmenopausal women: 1 mg PO daily starts on day 4 and continue until the day of definitive surgery (lumpectomy or mastectomy).

Tamoxifen for premenopausal women: 20 mg po daily starts on day 4 and continue until the day of definitive surgery (lumpectomy or mastectomy).

a: Within 6 days (preferably within 3 days) after the last dose of entinostat.

b: Tumor measurement: clinical tumor size, character, mobility, and location of the breast mass.

c: Chemistries: sodium, potassium, chloride, bicarbonate, BUN, creatinine, glucose, total bilirubin, calcium, total protein, albumin, AST (SGOT), ALT (SGPT), alkaline phosphatase, LDH, uric acid, phosphorus, and magnesium

d: Day 1: Prior to starting treatment
30 minutes after the first dose of entinostat

Day 15 (±1 day): BEFORE entinostat
30 minutes AFTER entinostat

e: Day 1: Prior to starting treatment

Day 15 (±1 day): BEFORE entinostat

f: Day 1: Prior to starting treatment

The day of definitive surgery (lumpectomy or mastectomy)

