11. MEASUREMENT OF EFFECT

For the purposes of this study, patients should be reevaluated weekly until the definitive surgery.

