11.2.1 Endpoint Definitions for Clinical Response (UICC criteria)

- Complete response (cCR) in the breast on physical exam will be defined as the absence of any palpable abnormality: i.e., no skin or breast thickening, mass, or associated skin or nipple changes. CR will be recorded separately for the breast and axilla.
- Partial response (cPR) in the breast will be defined as a 50% or greater decrease in the product of bipерpendicular diameters as measured with a ruler, compared with the prechemotherapy measurement.
- Stable disease (cSD) in the breast will be defined as palpable disease which does not fit the definition of PR or PD.
- Progressive disease (cPD) will be defined as an increase in the product of bipерpendicular diameters of 25% or greater compared to the original measurement.
- Inevaluable disease (cID) is defined as breast cancer that is not palpable in two dimensions.

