12.4 Analysis of Secondary Endpoints

Baseline and after treatment PR, HER2, EGFR, CK5/6, aromastase, tissue histone H3 and H4 acetylation will be treated as continuous variables. We may also use the multivariate analysis of variance to compare correlated biomarkers' expression. Correlation between biomarkers will be estimated and tested. The repeated measures model approach will be also used. Categorical outcome data (e.g., number of proteins expressed) will be recorded, proportions will be estimated and compared using the Fisher's exact test.

Clinical and pathological response rate with the corresponding 90% or 95% CI will be estimated for all eligible patients. The possible association between response rate and dose level will also be assessed.

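### First-cohort clinical response, and its link to dose level, is analysed only as a response rate although tumour size is recorded weekly; a supportive analysis of the measured change would recover an appreciable part of the information

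*Combined protocol and SAP*

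**What the plan says.** - **Objective.** Section 1.2, objective 3, covers clinical and pathological response to the preoperative combination. In practice this is the first cohort, treated for 15 to 29 days before surgery (Sections 5.1 and 5.4).
- **Definition.** Section 11.2.1 gives five clinical categories. Partial response is "a 50% or greater decrease in the product of bipерpendicular diameters as measured with a ruler"; progression is an increase of 25% or more; palpable disease between the two is stable disease. Complete response is the absence of any palpable abnormality.
- **Measurement.** Section 11 says that "patients should be reevaluated weekly until the definitive surgery". Footnote b of the first-cohort calendar (Section 10) lists what is recorded: "Tumor measurement: clinical tumor size, character, mobility, and location of the breast mass". The calendar marks this at pre-study, on Days 1, 8, 15, 22 and 29 while on treatment, and at surgery.
- **Analysis.** Section 12.4: "Clinical and pathological response rate with the corresponding 90% or 95% CI will be estimated for all eligible patients". The next sentence adds the dose analysis: "The possible association between response rate and dose level will also be assessed". No method is named for it.
- **Contrast.** For the biomarkers, the same section says that "tissue histone H3 and H4 acetylation will be treated as continuous variables" and names a repeated-measures model. No section plans an analysis of tumour size, or of its change, as a continuous variable.

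**The concern.** A fall of 50% in the product corresponds to about 29% in each diameter if both shrink equally (1 − √0.5 = 0.293). That is a demanding bar for two to four weeks of treatment. A tumour that shrinks by 40% and one that grows by 20% both enter the analysis as stable disease. Two diameters must be measured anyway to assign the category, so the finer information already exists at no extra burden. What is at stake is how much the trial can say about shrinkage, and about any relation to dose, from data it already collects. No go/no-go decision depends on it.

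**Working it through.** **1. The plan's own figures.** No power, null rate or variance is given for clinical response. The only response-rate design is the Simon rule in Section 12.1 for the biomarker composite (stop at 0/12; promising at ≥4/32; 5% v 20%). It reproduces: early stopping 0.95^12 = 0.540 and 0.80^12 = 0.069 (stated 0.54 and 0.07); power 0.866 (0.87); type I error 0.065 (0.07).

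**2. Information kept by a cut.** If the log size ratio is normal and a proportion q falls beyond the cut, the efficiency of the binary outcome is φ(z_q)² / [q(1 − q)]. For q = 20%: 0.280² / 0.16 = 0.49. For q = 10%: 0.34. For q = 5%: 0.22.

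**3. One-sample power, rates of 5% and 20% borrowed from the Simon design.** This is an assumption; those rates describe a different endpoint. On the log2 scale the cut is −1.
- No effect, 5% beyond the cut: SD = 1/1.645 = 0.608.
- Effect, 20% beyond the cut: mean = −1 + 0.842 × 0.608 = −0.488, a mean shrinkage of 1 − 2^(−0.488) = 29%.
- Standardised effect: 0.488/0.608 = 0.803.

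The binary power is the exact binomial tail at 20%. The continuous power uses the noncentral t with noncentrality 0.803√n, at the one-sided alpha that the binomial test attains.

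| n | responders needed | alpha | binary | continuous | share kept |
|---|---|---|---|---|---|
| 12 | 3 | 0.020 | 0.44 | 0.67 | 66% |
| 16 | 3 | 0.043 | 0.65 | 0.91 | 71% |
| 24 | 4 | 0.030 | 0.74 | 0.97 | 76% |
| 32 | 5 | 0.020 | 0.80 | 0.99 | 80% |

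**4. A wider range of assumptions.** SD of the natural-log ratio 0.30 / 0.45 / 0.60, n = 41. The t-test is two-sided at 0.05. The exact binomial test is at one-sided 0.025 or less, against the rate implied by zero mean change; part of its loss is discreteness.

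| mean shrinkage | continuous | binary |
|---|---|---|
| 10% | 0.59 / 0.31 / 0.20 | 0.08 / 0.09 / 0.06 |
| 20% | 1.00 / 0.87 / 0.64 | 0.43 / 0.41 / 0.26 |
| 30% | 1.00 / 1.00 / 0.96 | 0.92 / 0.86 / 0.66 |
| 40% | 1.00 / 1.00 / 1.00 | 1.00 / 1.00 / 0.95 |

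At matched alpha, with the SD of step 3 and n = 32, 20% shrinkage gives 0.42 binary against 0.80 continuous. So about half or more of the power goes at 20% shrinkage or less. The loss is 8 to 30 points at 30%, and 5 points or less at 40%.

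**5. Dose levels, same 5% v 20% assumption, two-sided 0.05.** The t-test noncentrality is 0.803√(n1·n2/(n1 + n2)); for 26 and 6 this is 0.803 × 2.208 = 1.77. The splits are assumptions.

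| split | t-test | Fisher, larger group at 20% | Fisher, smaller group at 20% |
|---|---|---|---|
| 26 / 6 | 0.40 | 0.00 | 0.15 |
| 20 / 12 | 0.57 | 0.05 | 0.19 |
| 16 / 16 | 0.59 | 0.10 | 0.10 |

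The binary comparison is weaker throughout, but for unequal splits the size of the gap depends on which group responds. The continuous comparison is not well powered either.

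**The case against.** Several objections have force.

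- **No powered test is weakened.** Section 12.4 plans an estimate with an interval, without a null rate or decision rule, and the go/no-go rests on the biomarker composite. A reader might infer that the trial could wrongly declare no clinical activity. The plan draws no such conclusion from this endpoint.
- **The loss is easily overstated.** A reader might infer that most of the power is lost. The table in step 3 shows the rate keeping 66% to 80% of it, and at 40% shrinkage almost nothing is lost. With no variance or target in the documents, the stronger statement cannot be supported.
- **The sample sizes are not first-cohort sizes.** 32 and 41 are totals over both cohorts; the first-cohort number is not fixed.
- **The dose comparison may not exist.** Level −1 opens only after dose-limiting toxicity or surgery delays. If only one combination is de-escalated, dose is largely confounded with endocrine partner and menopausal status. A continuous outcome cures neither problem.
- **A mean change is open to drift.** Size is taken by ruler, in an open-label single-arm study. On the model of step 3 at n = 32, an assumed 10% systematic drift with no drug effect gives a false positive in 0.248 of trials on the continuous scale and 0.115 on the binary scale, against a nominal 0.020.
- **Scope.** The rates in Section 12.4 include pathological response, which has no 50% cut. A log ratio is undefined for a clinical complete response.

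All of these stand as limits on the claim and on the remedy. None gives a reason to leave the measured change unanalysed.

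**Conclusion.** The point holds as a modest improvement, not as an error that threatens the trial. Section 12.4 uses only the response category for first-cohort clinical response and its association with dose, and so discards an appreciable part of the information on shrinkage over 15 to 29 days. At assumed response rates of 5% v 20%, the difference in one-sample power is 23 points at n = 12 (67 − 44) and 19 points at n = 32 (99 − 80). The share lost is greater for small mean shrinkage and close to nil for large. These sizes rest on a normal log ratio, borrowed response rates or an assumed SD and mean, and a test that the plan does not itself make; they illustrate the loss and are not predictions. The gain from modelling every weekly visit, rather than baseline and last visit, was not computed.

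**What to change.** In Section 12.4:

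1. Keep the UICC rates with their confidence interval as the defined response summary.
2. Add a supportive analysis for first-cohort tumours measurable in two dimensions at baseline: percentage change in the diameter product from baseline to the last pre-surgery visit, with a 95% CI. State which visit is baseline and whether the surgery-day examination counts as the last visit.
3. Fix the handling of clinical complete responses. Either count them as −100% with a median or rank-based summary, or fit the repeated-measures model already named in 12.4 to the log ratio with a stated floor value.
4. Label the result descriptive, because there is no control arm and the ruler measurements are unblinded.
5. Use the continuous change for the dose-level association only if both levels are populated. Label it exploratory, and account for endocrine partner where possible.

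The cost is SAP wording and a small amount of analysis; no visits, patients or measurements are added. The downside is that ruler measurements are noisy and open to systematic drift, and tumours not palpable in two dimensions do not contribute.

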12.5 Analysis of Exploratory Endpoints

- 12.5.1 To correlate the levels of histone H3 and H4 acetylation with the changes in Ki67 and ER, the appropriate to the data coefficient of correlation will be calculated. With 35 eligible subjects on the study we will have above 80% power to test the null hypothesis of some positive association against the research hypothesis of strong positive correlation, for instance, rho of 0.30 versus rho of at least 0.70.
- 12.5.2 To evaluate gene methylation profile, the outcomes of interest are gene methylation silencing and expression of candidate genes in tissue and in circulating DNA (ER-alpha, ER-beta, RAR-beta, cyclin D2, Twist, RASSF1A, and HIN-1) which are categorical and continuous respectively. Measurements of the baseline and change in gene methylation profile will be measured. The methylation silencing data for each gene will be tabulated and proportions will be estimated and compared using Fisher's exact test. For gene expression, exploratory plots, means and 95% confidence intervals will be calculated. We will use t-tests and signed-rank tests to determine whether or not the data shows evidence of change from baseline.

- 12.5.3 For the pharmacokinetic study, summary statistics (mean, standard deviation, median) and graphical techniques (boxplots, scatter-plots, histograms) will be used to characterize the behavior of pharmacodynamic (PD) and pharmacokinetic (PK) measurements. Regarding the exploratory endpoints of correlation between entinostat exposure and PD endpoints (i.e. acetylation of histone H3 and H4), A Mann-Whitney U test and logistic regression will be used to evaluate the association between entinostat exposure and PD endpoints as well as the change in Ki67 and ER expression as a categorical variable (i.e. response or no response). The entinostat exposure parameters explored will be plasma concentrations.
- 12.5.4 For the global gene expression analysis, we will have tissue samples from between 12-41 women enrolled in this study. Each of the tissue samples will be preprocessed using DASL assay from Illumina as described above. The resulting CEL files will be imported and stored on the Gene Traffic database in the Biostatistics Core (Core 4). Gene Traffic software will be used for quality control and identification of any experimental artifacts, including spatial patterns on chips. GCRMA will be applied to the CEL file results using the "Affy" library within the Bioconductor suite using R statistical software.⁴⁸ The GCRMA method summarizes probe set information to obtain one gene expression measurement per probe set on the array. Significance analysis of microarrays (SAM) will then be applied to the gene expression data to find genes which are differentially expressed between before and after treatment tissues.⁴⁹ The SAM statistic is similar to performing a two sample t-test for each gene under consideration, but it includes an adjustment to stabilize the coefficient of variation of the SAM statistic as a function of the standard deviation of the gene expression (across genes). As part of the SAM approach, a permutation method will be used to determine a cutoff for significance. Specifically, the permutation method takes the original data (the G x 6 matrix of expressions, where G is the number of genes) and permutes the data within each row of the expression matrix. The SAM analysis is then repeated on the permuted data. The distribution of the SAM statistics from the permuted analysis is called the "null" distribution, meaning that it is the distribution of SAM statistics we would expect to see if there were no relationship between gene expression and treatment (or, treatment modality). We then compare the distribution of the SAM statistics based on original data to the null distribution and choose a cutoff such that our false-discovery rate is 5%. That is, we choose a cutoff so that we would only expect that about 5% of the genes we claim to be differentially expressed would not be.

REFERENCES:

2. Holliday R: The inheritance of epigenetic defects. *Science* 238:163-70, 1987
3. Esteller M: Epigenetics in cancer. *N Engl J Med* 358:1148-59, 2008

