1.3. Exploratory Objectives

1. To correlate the levels of histone H3 and H4 acetylation in tumors with the changes in Ki67 and ER.
2. To evaluate baseline and change in gene methylation silencing and expression of candidate genes in tissues and in circulating DNA, including estrogen receptor (ER)-alpha, ER-beta, RAR-beta, cyclin D2, Twist, RASSF1A, and HIN-1.
3. To correlate entinostat trough concentrations with histone H3 and H4 acetylation in tumors as well as the change in Ki67 and ER.
4. To evaluate baseline and change in the global gene expression profile before and after treatment with entinostat and anastrozole/tamoxifen.

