- Ki-67: Will be assessed by counting 500 to 1000 cells, and will be reported as percent positive cells based on nuclear expression using ChromaVision ACIS system to quantify.
- EGFR: Will be assessed by counting 500 to 1000 cells, and will be reported as percent positive cells based on membrane expression using ChromaVision ACIS system to quantify.
- CK5/6: Will be assessed by counting 500 to 1000 cells, and will be reported as percent positive cells based on cytoplasmic expression using ChromaVision ACIS system to quantify.
- Aromatase: Will be assessed by counting 500 to 1000 cells, and will be reported as percent positive cells based on cytoplasmic expression using ChromaVision ACIS system to quantify.

Various other cancer specimens (expression in > 30% of the tumor cells) will be used as positive controls. Buffer will replace primary antibody for negative controls. All of the immunohistochemical staining will be quantitatively analyzed by ChromaVision ACIS system for immunohistochemistry image analysis. Quantitation of both staining intensity as well as assessment of numbers of positive stained cells will be determined by the agreement of a consensus of pathologists and researchers. These studies will be carried out under the direction of [name] in the Department of Pathology at University of Maryland.

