12. STATISTICAL CONSIDERATIONS

12.1 Study Design/Endpoints

This is a Pilot and Phase II, single-arm, open-labeled, multi-center study of entinostat in combination with anastrozole/tamoxifen in women with triple negative breast cancer. The main objective of this study is to assess the safety and efficacy of the combination of entinostat and anastrozole/tamoxifen. The primary endpoints, that we will use to evaluate the efficacy of the entinostat and anastrozole/tamoxifen, are the reduction in proliferative index (Ki67) and upregulation of ER after treatment with entinostat and anastrozole/tamoxifen therapy. We define patient's response as at least 50% reduction in the Ki67 index AND greater than 1% ER-positivity OR pathologic complete response in the post-treatment surgical specimens. For the evaluation of these biological endpoints, the analysis will include ALL of the patients in both cohorts (the first cohort-operable stage I-II and the second cohort-unresectable locally advanced/metastatic) as well as both anastrozole and tamoxifen groups.

In the pilot phase, the classic cohort-of-3-study design will be used. The primary endpoint of this part of the study is to determine the recommended dose for the phase II part as well as to evaluate the safety of both combinations. The dose levels are defined below for both pre- and postmenopausal groups. For safety, each combination (entinostat and anastrozole as well as entinostat and tamoxifen) will be evaluated separately. For both groups (anastrozole and tamoxifen), the first cohort of 3 patients will be treated starting at dose level 1 (d_1). If ≤ 1 patient experiences DLT, an additional 3 patients will be treated at this dose level (d_1). If ≥ 2 patients in the initial cohort of 6 patients suffer DLT, then up to 6 additional patients will be enrolled at the dose level -1. The phase II part will continue with the highest dose level with < 2 out of 6 patients experiencing a DLT. Therefore, we will need 6-12 patients for each combination

in this part of the study. The 6 patients from the pilot phase of each combination that are treated with the recommended dose level for the phase II will be included in the primary endpoint analysis.

The dose modification schemas are as follow for both postmenopausal and premenopausal women:

Dose Modification Schema for Postmenopausal Women		
Dose Level	Dose	
	Entinostat (mg)	Anastrozole (mg) daily
-1	3 mg weekly (on day 1, 8, 15, 22, and 29)	1

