1	5 mg weekly (on day 1, 8, 15, 22, and 29)	1

or

Dose Modification Schema for Premenopausal Women		
Dose Level	Dose	
	Entinostat (mg)	Tamoxifen (mg) daily
-1	3 mg weekly (on day 1, 8, 15, 22, and 29)	20
1	5 mg weekly (on day 1, 8, 15, 22, and 29)	20

In the phase II part, the Simon's two-stage design will be used for the study to ensure that the number of patients exposed to this new treatment is minimized. The analysis for this part of the study will include ALL of the patients in both cohorts (the first cohort-operable stage I-II and the second cohort-unresectable locally advance/metastatic) as well as both anastrozole and tamoxifen groups. The total sample size for the phase II part of the study is 32 with 12 and 20 patients in the first and second stage respectively. The 6 patients in the pilot phase of each combination that are treated with the recommended dose level for phase II will be included in the first stage of the phase II part of the study. The study will be terminated, if there is no response among the first 12 patients. If ≥ 1 response in these 12 patients is observed, then 20 more patients will be accrued. The combination will be considered promising, if ≥ 4 out of 32 patients have a response. This design yields 87% power. The probability of early stopping and declaring that this combination has no sufficient activity is 0.54, if the true success rate is 5% and 0.07 if the true response rate is 20%. If the true proportion of patients with Ki67 reduction combined with ER up-regulation is 0.20, the probability of concluding that the drug has sufficient activity is 0.87 and 0.07 if the true proportion is 0.05. To allow about 10% inevaluability, the phase II trial will accrue 35 eligible patients. Statistical analysis will be done using S-plus (TIBCO, version 8.0). All descriptive statistics will be reported. The multivariate analysis of variance or its non-parametric alternative will be applied to compare biomarkers' expression levels. The 90% confidence intervals will be constructed for the observed proportions. All statistical tests will be two-sided, and done at the 0.05 level of significance.

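### Section 12.5.3 tests entinostat concentration against Ki67 change only as response or no response, and applies two-group methods to continuous acetylation, which does not match objective 1.3.3

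*Combined protocol and SAP*

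**What the plan says.** The third exploratory objective in section 1.3 is: "To correlate entinostat trough concentrations with histone H3 and H4 acetylation in tumors as well as the change in Ki67 and ER". Section 12.5.3 is where that objective is analysed. It states: "A Mann-Whitney U test and logistic regression will be used to evaluate the association between entinostat exposure and PD endpoints", and continues "as well as the change in Ki67 and ER expression as a categorical variable (i.e. response or no response"). It adds: "The entinostat exposure parameters explored will be plasma concentrations". Summary statistics and scatter-plots of PK and PD measurements are also planned, but as description. No section adds a formal test of concentration against Ki67 or ER change on its measured scale.

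Other sections handle the same variables differently:

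- **Ki67 measurement, 9.1.3.1:** "Will be assessed by counting 500 to 1000 cells, and will be reported as percent positive cells based on nuclear expression".
- **Acetylation:** quantified by image analysis (9.1.3.4) and listed among the continuous variables in 12.4.
- **Ki67 and ER in 12.3:** analysed by a general linear model or Wilcoxon test.
- **12.5.1:** uses a correlation coefficient for acetylation against the same Ki67 and ER changes.

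Response has two candidate meanings. Section 12.1 defines a composite: "at least 50% reduction in the Ki67 index AND greater than 1% ER-positivity OR pathologic complete response". Section 11.1.1 defines each marker separately, as a Ki67 fall of at least 50% and ER staining of at least 1%. Section 12.5.3 does not say which it uses.

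**The concern.** The exposure variable is continuous, and so are Ki67 change and acetylation. A Mann-Whitney test or a binary logistic regression needs one side reduced to two groups. For Ki67 this throws away the size of the change on both sides of the cut. For acetylation the plan cannot be carried out as written: someone would have to choose a cut-point, possibly after seeing the data.

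At stake is the precision of one correlative aim. The trough sample and both biopsies are already collected, so an analysis that uses the measured values gets more from the same patients. It would also agree with the stated objective and with 12.5.1.

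**Working it through.** **Inputs from the documents.** Section 12.1 gives the phase II size: "The total sample size for the phase II part of the study is 32 with 12 and 20 patients" in the first and second stages. It gives response rates of 5% (null) and 20% (alternative), success at 4 or more of 32, and two-sided tests at 0.05. Section 12.3 uses 41 patients as the maximum for the biomarker analysis. Section 9.2.4.1 defines the day-15 pre-dose sample as the steady-state trough, and it is drawn in both stages.

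**The plan's own figures reproduce.** Section 12.5.3 states no power, so the check is on the figures around it.

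- Early stopping: 0.95^12 = 0.540 and 0.80^12 = 0.069 (stated 0.54 and 0.07).
- Probability of success, summed exactly over first-stage outcomes of 1 or more: 0.065 at 5% and 0.866 at 20% (stated 0.07 and 0.87).
- Section 12.5.1, 35 patients, correlation 0.30 versus 0.70, by Fisher's z: (0.867 − 0.310) × √32 = 3.15. Power is Φ(3.15 − 1.96) = 0.88 two-sided and 0.93 one-sided (stated above 0.80).

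**Number of responders, if the composite is meant.** Expected number = N × p.

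- 32 patients: 32 × 0.05 = 1.6 to 32 × 0.20 = 6.4.
- 41 patients: 41 × 0.05 = 2.05 to 41 × 0.20 = 8.2.

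Under this reading a first-stage stop leaves nothing to compare, because the rule is: "The study will be terminated, if there is no response among the first 12 patients". A rank correlation could still be computed on those 12 patients. If the per-marker definitions are meant, responders would usually be more numerous, because the biomarker part of the composite requires both markers.

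**Information kept when a normal outcome is cut at responder share p** is φ(z_p)² / [p(1 − p)].

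| Responder share | Kept | Lost |
|---|---|---|
| 50% | 0.637 | 36% |
| 20% | 0.490 | 51% |
| 12.5% (4 of 32) | 0.387 | 61% |
| 5% | 0.224 | 78% |

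A 50/50 split is the best case, so a cut of a normally distributed Ki67 change loses at least 36% under either meaning of response.

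**Power.** The documents give no exposure-Ki67 correlation, so a range is assumed. The simulation used a bivariate normal model, 32 patients, two-sided 0.05 and 6,000 runs per setting.

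| Assumed correlation | Spearman, continuous | Mann-Whitney, 50% responders | Mann-Whitney, 20% | Mann-Whitney, 5% |
|---|---|---|---|---|
| 0.3 | 0.36 | 0.24 | 0.20 | 0.06 |
| 0.4 | 0.58 | 0.41 | 0.32 | 0.12 |
| 0.5 | 0.80 | 0.62 | 0.48 | 0.18 |
| 0.6 | 0.94 | 0.81 | 0.66 | 0.25 |

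With 41 patients, correlation 0.5 and 20% responders, the figures are 0.90 against 0.58.

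**ER.** Section 3.1.4 requires baseline ER of 0 or below 1%, so ER change sits at a floor in patients who do not convert. With all non-responders placed at the floor (20% responders, 32 patients), Spearman against Mann-Whitney power is about 0.51 against 0.47 at correlation 0.5, and 0.34 against 0.32 at 0.4.

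**The case against.** The best defence is that the aim is exploratory, carries no power claim and drives no dose, stopping or success decision. The Ki67 cut also has a documented reason: section 2.6 reports that a change of at least 32-50% is needed to attribute it to treatment in one patient, and then adopts 50%. That reason concerns classifying an individual. It does not make the cut efficient for studying a relation across patients, so it supports keeping the responder comparison but not relying on it alone.

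A reader might infer more than the documents support, in four ways:

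- **Half the information is lost for both markers.** The 51% figure belongs to a normal outcome with 20% responders. It does not carry over to ER, where the floor leaves little to lose in the setting simulated.
- **There will be only a handful of responders.** That is so for the composite at the design rates. Section 12.5.3 may mean the per-marker definitions, for which no rate is given.
- **A real relation would be missed.** This depends on an unknown correlation. At 0.6 the planned test has power 0.66 with 20% responders. At 0.3 the better test reaches only 0.36.
- **Logistic regression is unusable.** Only one predictor is named, and the Mann-Whitney test stays valid with few responders. The responder count is a reason for caution and does not show that the method fails.

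One practical objection also stands. A patient with pCR has no residual invasive tumour in which to measure Ki67, so a continuous analysis needs a rule for her.

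**Conclusion.** The point holds for Ki67 and for the acetylation method. Section 12.5.3 does not deliver the correlation named in objective 3 of section 1.3, differs without explanation from 12.5.1, and leaves both the acetylation cut-point and the meaning of response undefined. For Ki67 the information loss is between 36% and 78%, depending on a responder share that the text does not fix. The power comparison also rests on a bivariate normal model and an assumed correlation. For ER the case is weak. The consequence is lost precision and an avoidable analyst choice in an exploratory aim, and the two-stage decision rule is not touched.

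**What to change.** In 12.5.3:

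1. Name the day-15 pre-dose concentration as the exposure variable for this objective.
2. Make Spearman correlation of that trough with continuous H3 and H4 acetylation, and with the continuous log ratio of post- to pre-treatment Ki67, the main exploratory analysis, with a linear model as support.
3. Rank patients with pCR and no measurable residual tumour as having the largest Ki67 reduction in the Spearman analysis.
4. Keep the response/no-response comparison as supportive, and use it for ER. State whether response is the composite of 12.1 or the per-marker definition of 11.1.1. If per-marker, give the ER threshold, since 9.1.3.1 uses 5% for a positive result and 11.1.1 uses 1%.

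The cost is a wording change and slightly more analysis work. No extra samples, patients or visits are needed.
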